3) *Light transmittance aggregometry (LTA):* Platelet aggregation will be performed using LTA according to standard protocols. LTA will be assessed using platelet-rich plasma (PRP) by the turbidimetric method in a 2-channel aggregometer (Chrono-Log 490 Model, Chrono-Log Corp., Havertown) as previously described (3). Platelet agonists will include arachidonic acid (AA; 1 mM), collagen (3µg/ml) and ADP (5 and 20 µM) and TRAP (15 µM). PRP will be obtained as a

supernatant after centrifugation of citrated blood at 1000 rpm for 10 minutes. The isolated PRP will be kept at 37° C before use. Platelet-poor plasma (PPP) will be obtained by a second centrifugation of the blood fraction at 2800 rpm for 10 minutes. Light transmission will be adjusted to 0% with the PRP and to 100% for the PPP for each measurement. Curves will be recorded for 6 minutes and platelet aggregation will be determined as the maximal percent change (MPA) and late platelet aggregation (LPA) in light transmittance from baseline using PPP as a reference.

PK assessments

PK assessments will include determination of plasma concentration of clopidogrel active metabolite, ticagrelor and its active metabolite (AR-C124910XX), as previously described (3,26). Time for the maximum plasma concentration (T_{max}), maximum observed plasma concentration (C_{max}) and the area under the plasma concentration vs. time curve from time 0 to the last measurable concentration (AUC_{0-t}) will be calculated.

Other laboratory assessments

Blood samples will also be collected to assess the following parameters: a) HbA1c at baseline; b) reticulated platelets at baseline and 30 days; c) troponin levels at baseline, and 6 h and 24 h post PCI.

Study endpoints, sample size calculation and statistical analysis

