The primary endpoint of our study will be platelet reactivity, measured as PRU level using VN, of ticagrelor versus clopidogrel MD at 30 days after PCI, immediately pre-dosing dosing (trough levels). Based on previous studies (22,24,27), assuming a standard deviation of 55 and 100 PRU for ticagrelor and clopidogrel, respectively, a sample size of 34 patients (17 per treatment group) will be needed to detect an absolute difference of 95 PRU between ticagrelor and clopidogrel (corresponding to means of 170 versus 75) with a 90% power and a 2-tailed alpha value of 0.05. Assuming a potential 25% in data attrition due to patient drop-out (e.g., due to side effects, unplanned use of parenteral antiplatelet therapies after randomization or withdrawal of consent) or invalid PD samples (e.g, due to hemolysis or technical reasons), a sample size of approximately 42 patients is expected to be randomized.

Conformity to the normal distribution will be evaluated for continuous variables with the Shapiro-Wilk test. For baseline characteristics, continuous variables will be expressed as mean (standard deviation [SD]) and categorical variables as frequencies and percentages. Chi-squared test or Fisher's exact test will be used where appropriate to compare categorical variables between 2 groups.

The PD population will include all patients with PD data and without a major protocol deviation thought to affect significantly the PD of ticagrelor or clopidogrel. The PD population will be used for analysis of all primary and secondary PD variables. Erroneously treated patients (eg, those randomized to one treatment but actually given the other) will be accounted for based on the actual treatment received.

The primary analysis of the difference between ticagrelor and clopidogrel in PRU will be analyzed using analysis of variance. Treatment level means and 2-sided 95% confidence intervals (CIs) will be estimated. Analysis of variance will also be used to evaluate other intergroup comparisons. Repeated measures of analysis of variance, taking into account between- and within-subject variations, will be conducted to evaluate the impact of the 2 different treatments on platelet reactivity across time points. A p-value < 0.05 will be considered statistically significant. Statistical analysis will be performed with SPSS version 24 software (SPSS Inc.).

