Secondary endpoints will include comparisons of measures of platelet reactivity using VN, VASP, and LTA at all other time points [0.5 h, 8 h, 24 h (trough and peak), 30 days (trough and peak) following LD, and end of PCI] as well as rates of high on-treatment platelet reactivity (HPR). In line with recent expert consensus definitions, HPR will be defined as a PRU >208, VASP-PRI > 50%, maximum LTA response to 20 μ M ADP > 59 %, maximum LTA response to 5 μ M ADP > 46 % (28). In addition, time for the maximum plasma concentration (T_{max}), maximum observed plasma concentration (C_{max}) and the area under the plasma concentration vs. time curve from time 0 to the last measurable concentration (AUC_{0-t}) of plasma concentration of clopidogrel active metabolite, ticagrelor and its active metabolite (AR-C124910XX) will be calculated.

All patients who received at least 1 dose of study drug will be included in the safety population. Safety will be evaluated by assessment of adverse events (including bleeding and ischemic), serious adverse events, physical examination, and vital signs. Adverse events will be collected up to 7 days after the completion of the study. Bleeding events will be classified according to BARC (Bleeding Academic Research Consortium) criteria (29). Stent thrombosis

will be classified according to ARC (Academic Research Consortium) definitions (30). MI, including peri-procedural MI, will be defined according to the universal definition (31). Ischemic stroke will be defined as an ischemic cerebral infarction caused by an embolic or thrombotic occlusion of a major intracranial artery. Death will be considered cardiac in origin unless obvious non-cardiac causes can be identified.

Possible Discomforts and Risk

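### The p<0.05 rule is not limited to the primary test and covers up to 111–127 secondary platelet comparisons, with no ranking, error control or nominal label

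*Combined protocol and SAP*

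**What the plan says.** All references are to the combined protocol and SAP.

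- **Primary test** (Study endpoints, sample size calculation and statistical analysis). There is one endpoint: "The primary endpoint of our study will be platelet reactivity, measured as PRU level using VN", at the 30-day trough. It is sized "with a 90% power and a 2-tailed alpha value of 0.05".
- **Significance rule** (same section). After naming ANOVA for the primary and for the other between-group comparisons, and repeated-measures ANOVA across time points, the plan says: "A p-value < 0.05 will be considered statistically significant". Nothing limits this to the primary test.
- **Secondary endpoints** (same section). "Secondary endpoints will include comparisons of measures of platelet reactivity using VN, VASP, and LTA at all other time points". Seven post-load times are listed. HPR rates follow, with four cut-offs: PRU, VASP-PRI, and LTA with 20 µM and 5 µM ADP.
- **LTA readouts** (PD assessments). "Platelet agonists will include arachidonic acid (AA; 1 mM), collagen", plus ADP at two concentrations and TRAP, which makes five agonist conditions. Each is read twice: "platelet aggregation will be determined as the maximal percent change (MPA) and late platelet aggregation (LPA) in light transmittance".
- **Sampling** (Study design). There are nine samples: baseline and eight after the load. One of the eight is a 2 h sample that the secondary-endpoint list leaves out.

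The documents do not order the secondary endpoints, adjust for multiplicity, or call any of these tests nominal or exploratory.

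**The concern.** This is more than missing detail. The plan gives an explicit decision rule, and followed literally it lets any secondary p-value below 0.05 be reported as a significant difference between ticagrelor and clopidogrel. An isolated p of 0.03 for collagen late aggregation at 8 h would have the same standing as a planned VASP result at day 30.

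Platelet function results are the main output of this trial. The Possible benefits section says the study is not designed to assess clinical benefit and that differences in antiplatelet profile may prompt a larger trial. With about 42 patients and many readouts, a reader could not tell a planned secondary finding from one selected out of a large set.

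The risk is greatest where a true difference between arms is least expected. Both arms receive aspirin, and the randomised drugs are both P2Y12 inhibitors. VerifyNow, VASP and ADP-induced aggregation should therefore differ for real. Responses to arachidonic acid, collagen and TRAP may not differ, and these readouts supply six comparisons at every time point.

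**Working it through.** **1. The plan's own figure.** Inputs: "assuming a standard deviation of 55 and 100 PRU for ticagrelor and clopidogrel, respectively" and "to detect an absolute difference of 95 PRU between ticagrelor and clopidogrel", two-sided alpha 0.05.

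- Root-mean-square SD = √((55² + 100²)/2) = 80.7.
- With 17 per arm, the noncentrality is 95 / (80.7 × √(2/17)) = 3.43 on 32 degrees of freedom. Power is 91.4% by the pooled t-test and 90.9% by Welch.
- With 16 per arm, pooled power is 89.6%.

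So 17 per arm (34 in total) reproduces, and the primary test is sound at 0.05.

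**2. Counting the secondary tests.** Readouts per time point: PRU (1) + VASP-PRI (1) + 5 LTA conditions × 2 = 12. Let T be the number of post-load times: 7 as listed for the secondary endpoints, 8 if the 2 h sample is included.

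| | T = 7 | T = 8 |
|---|---|---|
| Continuous: 12T − 1 primary | 83 | 95 |
| HPR: 4T | 28 | 32 |
| Between-arm total | 111 | 127 |
| Adding 12 repeated-measures analyses | 123 | 139 |

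This is the fullest reading. A narrow one (maximal aggregation only, no HPR, no repeated measures) still gives 7 readouts × 7 times − 1 = 48.

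**3. Expected chance findings.** Only the non-P2Y12 agonists are treated as null: 3 agonists × 2 readouts × T = 42 or 48 tests.

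- Expected false positives = 0.05 × 42 = 2.1, or 0.05 × 48 = 2.4. This holds whatever the correlation.
- Under independence, P(at least one) = 1 − 0.95^42 = 88.4%, or 1 − 0.95^48 = 91.5%.

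**4. Allowing for correlation.** The tests share patients, and the two LTA readouts come from the same curve. The documents give no correlations, so these are assumed. Simulation: 17 per arm, two-sample t-tests, 6,000 trials per setting.

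| Correlation: agonists / two LTA readouts / times | 42 tests | 48 tests |
|---|---|---|
| 0.2 / 0.7 / 0.3 | 80% | 83% |
| 0.3 / 0.8 / 0.5 | 70% | 74% |
| 0.3 / 0.9 / 0.7 | 55% | 58% |
| 0.5 / 0.9 / 0.7 | 52% | 54% |
| 0.5 / 0.95 / 0.9 | 33% | 35% |

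The probability of at least one chance finding is thus roughly 35–80%. The mean number stays near 2.1 or 2.4 throughout.

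**5. Would PRU-based HPR serve as a first key secondary?** Assume normal PRU values with the plan's means (170 and 75) and SDs.

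- Clopidogrel: P(PRU > 208) = 1 − Φ((208 − 170)/100) = 1 − Φ(0.38) = 35%.
- Ticagrelor: 1 − Φ((208 − 75)/55) = 1 − Φ(2.42) = 0.8%.
- Power of Fisher's exact test at 0.05: 67% with 16 per arm (about what 42 × 0.75 = 31.5 evaluable patients gives) and 72% with 17.

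**The case against.** A reader might infer that chance significant findings are near certain. The documents do not support that. A figure of 99.8–99.9% needs all 123–139 tests to be both independent and truly null. Neither holds: the plan itself assumes a 95 PRU difference on the main P2Y12 readout, and the measurements are repeated on the same patients.

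The count can also be challenged. The plan does not say that both LTA readouts of every agonist enter the comparisons, that HPR is tested at every time, or that a repeated-measures analysis is run for each readout. This stands, so 111–127 and 123–139 are upper bounds. But the openness is part of the problem, because nothing limits which comparison may be called significant.

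The null status of arachidonic acid, collagen and TRAP is stated nowhere. If stronger P2Y12 inhibition changes any of these responses, fewer tests are null and the expected number falls. If only arachidonic acid were null (14–16 tests), it would be 0.7–0.8.

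Finally, this is a small mechanistic trial with one primary test, and the other endpoints are already called secondary. It would be wrong to infer that the primary conclusion is compromised, and formal adjustment of every readout is not needed. But the word secondary does not switch off a significance rule written for all tests.

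**Conclusion.** The point holds in a limited form. The plan grants significance to any p-value below 0.05 across a large, unranked secondary set of up to 111–127 between-arm comparisons (123–139 with repeated-measures analyses). The primary test is unaffected; what is at stake is how the secondary findings may be described.

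About two chance findings (2.1–2.4) are to be expected if the arachidonic acid, collagen and TRAP responses do not differ between arms. The probability of at least one is roughly 35–80% under the correlations assumed here and about 90% under independence. These figures rest on three assumptions outside the documents: the null status of those agonists, the correlations, and the fullest reading of which tests will be run. The absence of any limit on the significance rule rests on the text alone. The change should be made, but the design does not depend on it.

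**What to change.** In the statistics section, restrict the term statistically significant to the primary day-30 trough PRU comparison. Report all secondary platelet-function and HPR comparisons as estimates with 95% confidence intervals and p-values labelled nominal. That is enough on its own.

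If the sponsor wants confirmatory secondary claims, add a short ordered list, each tested at 0.05 only if the primary and every earlier step succeeded. Start with continuous P2Y12 readouts, for example VASP-PRI and then maximal aggregation to 20 µM ADP, both at the day-30 trough. The documents give no means or SDs for these, so their power should be confirmed first. PRU-based HPR should not lead the list: at 67–72% power it would stop the sequence 28–33% of the time even if the plan's assumptions are right.

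In the same edit, state whether the 2 h sample belongs to the secondary comparisons, so that the sampling schedule and the endpoint list agree.

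The cost is about two sentences, with no change to patients, samples, assays or sample size. The downside is that fewer secondary results can be called significant.
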